## 6 Adverse Events

### 6.1 Adverse Events (AEs)

An adverse event (AE) is any untoward occurrence in a subject, whether or not related to the product. An AE does not necessarily have to have a causal relationship with the study treatment. AEs include events not present at baseline and events that worsened if present at baseline. Hospitalizations for pre-treatment conditions (e.g., elective cosmetic procedures) or surgeries that were planned prior to entry into the study are not considered adverse events. Adverse events, regardless of causality, will be captured from the signing of the Informed Consent Form and for the duration of the subject's participation. Events will be captured as observations from investigator or events reported by subjects from the signing of the informed consent form.

### 6.2 Serious Adverse Events (SAEs)

A **serious adverse event** (SAE) is any untoward medical occurrence that meets one or more of the following criteria according to federal regulations:

- a. results in death;
- b. is life-threatening (the subject was at risk of death at the time of the event. It does not refer to an event, which hypothetically might have caused death if it were more severe);
- c. results in persistent or significant disability or incapacity;
- d. requires inpatient hospitalization or prolongation of existing hospitalization;
- e. is a congenital anomaly or birth defect;
- f. is considered an important medical event (may not be immediately life-threatening or result in death or hospitalization but may jeopardize the subject or may require intervention to prevent one of the outcomes listed in the definition above).

#### 6.2.1 SAE Reporting

An **Adverse Event or Suspected Adverse Reaction** is considered "serious" if, in the view of either the investigator or sponsor, it results in any of the following outcomes:

- Death;

- A life-threatening adverse event; (Note: the term “life-threatening” as used here refers to an event in which the patient was at risk of death at the time of the event; it does not refer to an event which hypothetically might have caused death if it were more severe);
- In-patient hospitalization or prolongation of existing hospitalization;
- A persistent or significant disability/incapacity (substantial disruption of the ability to conduct normal life functions);
- A congenital anomaly/birth defect;
- Any “other” important medical event.

Important medical events that may not result in death, be life-threatening or require hospitalization may be considered Serious Adverse Events when, based on appropriate medical judgment, they may jeopardize the patient and may require medical or surgical intervention to prevent one of the outcomes listed in this definition.

Adverse events will be reported as per local guidelines.

### **6.3 Pregnancy Reporting**

The investigator will follow the pregnancy and outcome. Any information gained will be documented in the subject source documents and reported as per local guidelines. Female subjects who become pregnant will be discontinued from study treatment.

## **7 INVESTIGATIONAL PRODUCT HANDLING**

### **7.1 Investigational Product Receipt**

At study initiation and as needed thereafter, tralokinumab will be shipped to a responsible person at the investigator's institution, who will check the amount and condition of the drug, and maintain a record of this information.

### **7.2 Investigational Product Storage**

#### **7.2.1 Tralokinumab Storage**

Tralokinumab will be stored between 2-8 degrees Celsius. The study site will monitor and record daily temperatures during business days. At the study site, all IP will be stored in a locked, safe area to prevent unauthorized access.

## **8 RECORD RETENTION**

The investigator must retain these documents according to local laws or requirements. Essential documents include, but are not limited to, the following:

- Signed informed consent documents for all subjects;
- Subject screening and enrollment log;
- Record of all communications between the Investigator and the IRB/EC
- List of Sub-investigators and other appropriately qualified persons to whom the Investigator has delegated significant study-related duties, together with their roles in the study, curriculum vitae, and their signatures;
- Copies of CRFs (if paper) and of documentation of corrections for all subjects;
- IP accountability records;
- All other source documents (subject records, hospital records, laboratory records, etc);
- Essential Documents for the Conduct of a Clinical Trial.

### **8.1 Study Monitoring**

The investigator will self-monitor all study records for accuracy, completeness, and compliance with the protocol and GCPs and federal regulations. Study site facilities and study records will be made available to regulatory authorities' inspectors if an inspection takes place.

### **8.2 Statistics**

It is desired to have approximately n=20 subjects at randomization. Analysis will be performed by the Investigator for IGA, BSA, DLQI, Pruritis NRS. The Investigator will also analyze AE's and SAE's.

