### **5.4 Subject Enrollment and Treatment Assignment**

20 subjects of either gender with moderate-to severe atopic dermatitis will be enrolled to receive open-label tralokinumab

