## **5.6 Study Procedures**

### **5.6.1 Informed Consent**

This Study will be conducted in compliance with CFR Title 21, Part 50 (Informed Consent of Human Subjects). Informed consent will be obtained from each subject in writing before participation in the Study. A signed copy of the Informed Consent Form will be provided to each subject. A provision to obtain a signed authorization to provide protected health information to the study sponsor, internal quality assurance agencies, health insurance agencies, and other parties as specified in the Federal Health Insurance Portability and Accountability Act (HIPAA) privacy regulation will be included in the Informed Consent Document. HIPAA authorization is voluntary. However, since the use and release of health information is critical to the conduct of the study, subjects who do not provide authorization to use and disclose their health information will not be enrolled into the study. Subjects who withdraw their authorization to use and release health information during study participation will be formally discontinued from the study. The investigator may use and release at any time all the information collected prior to a subject's withdrawal of the authorization to all authorized parties to satisfy scientific, regulatory, and financial concerns.

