### **5.6.11 Early Discontinuation Procedures**

Subjects will be prematurely discontinued from the study under the following conditions:

1. Subject requests to withdraw from the study.
2. Subject is noncompliant with protocol schedule, restrictions, and/or requirements.
3. Subject experiences an adverse event that makes it difficult or intolerable for the subject to continue treatment, or increases risk to the subject, or interferes with the investigator's ability to clinically evaluate the progress of the subject's treatment.
4. Subject begins an unapproved concomitant therapy for atopic dermatitis or another medical condition that may increase risk to the subject if continuing study treatment.
5. Subject cannot be reached / lost to follow-up.
6. The study investigator suspends or terminates the study.
7. Other unanticipated reason.

Any subject who prematurely discontinues the study should complete the week 24 (End of Study) assessments. Any subject who withdraws consent to participate in the study will be removed from further treatment and/or study observation immediately upon the date of request.

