#### **Primary Endpoints:**

Proportion of subjects achieving an IGA score of 0 or 1 at week 16

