#### **8.2.1 Additional Statistical Considerations**

Additional statistical procedures may be detailed in and performed according to a separate statistical plan at the discretion of sponsor-investigator.

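### Does the lack of a stated denominator and missing-score rule for the week-16 IGA 0/1 proportion call for a change to section 8.2?

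*Combined protocol and SAP*

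**What the plan says.** The analysis plan is section 8.2 with its endpoint lists, plus 8.2.1. It names the investigator as analyst and lists the variables. It gives one count, "It is desired to have approximately n=20 subjects at randomization", and one primary endpoint, "Proportion of subjects achieving an IGA score of 0 or 1 at week 16". It defines no analysis set and does not say how a subject without a score is handled. Section 8.2.1 adds "Additional statistical procedures may be detailed in and performed according to a separate statistical plan at the discretion of sponsor-investigator", which permits a further document without requiring one. The documents do not show whether one exists.

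Elsewhere the population is described consistently. The Synopsis (Study Design) and section 5.1 have 20 subjects receiving tralokinumab, and section 5.4 says that 20 subjects "will be enrolled to receive open-label tralokinumab".

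Three places foresee incomplete data. In section 5.6.11 a subject who withdraws consent "will be removed from further treatment and/or study observation immediately upon the date of request". Section 5.6.1 says "Subjects who withdraw their authorization to use and release health information during study participation will be formally discontinued from the study". Section 5.6.11 also lists loss to follow-up and study termination. For those who leave early it says "Any subject who prematurely discontinues the study should complete the week 24 (End of Study) assessments", and the Schedule of Assessments has no early-termination column. On stopping the drug, section 5.5.1.3 allows temporary or permanent discontinuation for a related adverse event, with standard care after a permanent stop. Section 6.3 says "Female subjects who become pregnant will be discontinued from study treatment".

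**The concern.** A proportion needs a numerator rule and a denominator, and section 8.2 spells out neither for an incomplete subject. Its only count is tied to an event that a single-arm study does not have. If d of the 20 subjects have no week-16 IGA, both x/20 and x/(20 − d) fit the wording. The second is never lower, and it is probably too high where subjects stop because they are doing badly.

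Two further questions follow. A subject who stops tralokinumab but stays under observation might have a week-16 score obtained on other treatment. An exit score taken well before week 24 might be filed under week 24, where IGA 0/1 and a 50% BSA reduction are secondary endpoints. The data are open-label and the investigator analyses them, so an unwritten choice could be made after the results are known. The primary efficacy estimate would be what is at stake.

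**Working it through.** **The plan's own figure.** The 20 cannot be re-derived, because the documents give no reference rate, target rate, precision, power or dropout rate. It is not in dispute here.

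**Step 1: who is in the denominator.** The Synopsis, 5.1 and 5.4 all describe 20 subjects given the drug. There is no allocation step anywhere. Read together with the endpoint line, the randomization wording can only mean enrolment. All enrolled and treated subjects is the plain reading.

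**Step 2: effect of dropping unscored subjects at week 16.** Inputs: n = 20 (section 5.4). The values of x (responders) and d (no score) are assumptions.

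Shift = x/(20 − d) − x/20 = x·d / [20·(20 − d)].

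Exact (Clopper-Pearson) limits for x/n are the 2.5% point of Beta(x, n − x + 1) and the 97.5% point of Beta(x + 1, n − x).

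| x | x/20 (95% CI) | d=1 | d=2 | d=3 | d=4 | d=5 |
|---|---|---|---|---|---|---|
| 2 | 10.0% (1.2 to 31.7) | 10.5 | 11.1 | 11.8 | 12.5 | 13.3 |
| 6 | 30.0% (11.9 to 54.3) | 31.6 | 33.3 | 35.3 | 37.5 | 40.0 |
| 10 | 50.0% (27.2 to 72.8) | 52.6 | 55.6 | 58.8 | 62.5 | 66.7 |

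The smallest shift is 2·1/(20·19) = 0.5 points and the largest is 10·5/(20·15) = 16.7 points. Every entry lies inside the interval for its x/20. That has a limit: ten responders with seven missing would give 10/13 = 76.9%, above 72.8%. It would take more than a third of the study unscored.

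**Step 3: off-treatment scores at week 16.** Adverse events are the only trigger that section 5.5.1.3 names for stopping the drug. Section 5.6.11 takes a subject out of the study when an adverse event makes continuing treatment difficult or intolerable (item 3), and when an unapproved therapy for atopic dermatitis is begun (item 4). So most routes to other treatment are also routes out of the study, and they leave a missing score rather than an off-treatment one. The cases that clearly remain are pregnancy (6.3), a temporary interruption, and an adverse-event stop that falls short of item 3.

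An illustration with two such subjects: 15 on-treatment scores with 6 responders, 2 off-treatment scores with k responders, and 3 with no score.
- Missing and off-treatment both counted as non-response: 6/20 = 30.0%.
- On-treatment scores only: 6/15 = 40.0%.
- All observed scores: (6 + k)/17 = 35.3%, 41.2% or 47.1% for k = 0, 1, 2.

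All lie within 11.9 to 54.3%. No passage supports two as a likely number.

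**Step 4: exit scores and week 24.** Section 5.6.11 says which assessments an early leaver completes and is silent on analysis. The Synopsis and section 8.2 define the responder endpoints at week 24. A score taken at, say, week 6 is not a week-24 score.

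If one were nonetheless used, take 6 responders among 16 completers and 4 exits with k responders. Then (6 + k)/20 = 30, 35, 40, 45 or 50% for k = 0 to 4, against 6/16 = 37.5% in completers. All lie within 11.9 to 54.3%. An extreme case does go outside: 8 responders among 14 completers, with six exits all scoring 0 or 1, gives 14/20 = 70.0% against 8/20 = 40.0% (19.1 to 63.9). It needs six exits, all responders, and a reading that the endpoint definition does not invite.

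**The case for a change.** The strongest reply is that sampling uncertainty does not excuse an undefined estimate. With no test and no comparator, the week-16 proportion is the efficacy result. The investigator analyses it (8.2) and self-monitors the records (8.1) in an open-label study, and dropping unscored subjects can only hold the rate or raise it. Even with the denominator fixed at 20, the text does not say whether a missing score is a non-response, imputed or set aside. At 20 subjects, each one is worth 5 points.

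Much of this stands. The omission is real, nothing elsewhere in the documents fills it, and lying inside a wide interval does not make a bias harmless. It does not follow that the plan is wrong. An unwritten policy differs from a stated rule that misleads, and the text already leans to all 20 subjects. The choice is also easy to see through: once responders, subjects scored and subjects treated are reported, a reader can form either rate. The off-treatment and week-24 parts are weaker. The first overlooks how much section 5.6.11 removes from the study, and the second rests on one of two readings, the less natural one.

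**Conclusion.** No change is called for. The randomization wording is a clerical slip in a single-arm study. The absent missing-score rule is a gap that a competent analyst fills in the usual way: all treated subjects in the denominator, with the number actually scored shown. Section 8.2.1 leaves room for that to be written down. Sections 3.2 and 4 describe the aim as exploring effectiveness and safety, and no planned test or decision turns on the choice.

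For one to five missing scores and 2, 6 or 10 responders, the choice moves the rate by 0.5 to 16.7 points, always within the exact 95% interval for x/20. A middling case is 30.0% against 35.3%. All response and dropout counts are assumptions. The conclusion also rests on modest loss before week 16. With seven or more of 20 unscored and a high response rate, the two rates could differ by more than the interval allows, and that would need comment when results are reported.

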#### **Primary Endpoints:**

Proportion of subjects achieving an IGA score of 0 or 1 at week 16

#### **Secondary Endpoints:**

Proportion of subjects achieving IGA 0 or 1 at weeks 4, 8, 12, 20, 24

Proportion of patients achieving 50% reduction in BSA at weeks 12, 16, 20 and 24

IGA, BSA, Pruritis NRS and DLQI improvement at weeks 0, 4, 8, 12, 16, 20 and AE's/SAE's

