Main Exclusion Criteria	
Subjects who meet any of the following criteria will be excluded from participation in this study:
 
 
1. Subjects with previous exposure to tralokinumab.
 
2. Known or suspected hypersensitivity to tralokinumab or any of its excipients.
 
3. Women of childbearing potential who are pregnant, intend to become pregnant, or are lactating.
 
4. Use of tanning beds or phototherapy within 4 weeks of baseline
 
5. Use of systemic therapies (systemic steroids, cyclosporine, oral JAK inhibitors etc.) for atopic dermatitis within 4 weeks
 
6. Patient non-compliant with Dupixent dosing based on investigator discretion.
 
7. Any clinically significant (as determined by the investigator) cardiac, endocrinologic, pulmonary, neurologic, psychiatric, hepatic, renal, hematologic, immunologic disease, or other major disease that is uncontrolled.
 

Study Visits	
Screening
 
Week 0
 
Week 4
 
Week 8
 
Week 12
 
Week 16
 
Week 20
 
Week 24

Study Endpoints	
Primary Endpoints:
 
Proportion of subjects achieving IGA 0 or 1 at week 16
 
Secondary Endpoints:
 
Proportion of subjects achieving IGA 0 or 1 at weeks 20, 24
 
Proportion of patients achieving 50% reduction in BSA at weeks 12, 16, 20 and 24
 
IGA, BSA, Pruritis NRS and DLQI improvement at weeks 0, 4, 8, 12, 16, 20 and 24
 
Adverse Events/Serious Adverse Events (SAE's)

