### **5.6.6 Investigator's Global Assessment (IGA)**

IGA will be determined for all subjects throughout the study. The Investigator's Global Assessment of atopic dermatitis is scored on a 5-point scale (0-4), evaluating global erythema, induration and scaling. [See Appendix A](#)

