### **5.6.8 Body Surface Area (BSA)**

BSA will be determined for all subjects throughout the study. The subjects palm will be selected for the measuring unit of body surface area. The physician will equate the number of palms affected by atopic dermatitis to derive the BSA total.

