### **5.6.10 Patient Reported Outcomes**

#### **5.6.10.1 Dermatology Life Quality Index (DLQI)**

Subjects will complete the Dermatology Life Quality Index (DLQI) at weeks 0, 4, 8, 12, 16, 20 and 24. [See Appendix B](#)

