### Schedule of Assessments

Procedure	Screening	BASELINE	Week4	Week 8	Week 12	Week 16	Week 20	Week 24
Informed Consent	X							
Demographics/Medical History	X	X						
Inclusion/Exclusion	X	X						
Physical Exam	X	X		X	X	X	X	X
Concomitant Medications	X	X	X	X	X	X	X	X
Adverse Events	X	X	X	X	X	X	X	X
Urine Pregnancy Test	X	X						
BSA	X	X		X	X	X	X	X
IGA	X	X		X	X	X	X	X
Itch NRS		X	X	X	X	X	X	X
DLQI		X		X	X	X	X	X
Vital Signs	X	X		X	X	X	X	X
Photography		X		X	X	X	X	X
IP Dispensing and Accountability		X	X	X	X	X	X	X

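### Week-4 IGA, BSA and DLQI are secondary endpoints but are not in the Schedule of Assessments, and the synopsis and Section 8.2 give different secondary lists; the week-16 primary endpoint is unaffected

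*Combined protocol and SAP*

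**What the plan says.** The secondary endpoints appear twice.

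- **Synopsis, Study Endpoints:** "Proportion of subjects achieving IGA 0 or 1 at weeks 20, 24" and "IGA, BSA, Pruritis NRS and DLQI improvement at weeks 0, 4, 8, 12, 16, 20 and 24".
- **Section 8.2, Secondary Endpoints:** "Proportion of subjects achieving IGA 0 or 1 at weeks 4, 8, 12, 20, 24" and "IGA, BSA, Pruritis NRS and DLQI improvement at weeks 0, 4, 8, 12, 16, 20 and AE's/SAE's".

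Both also list a 50% reduction in BSA at weeks 12, 16, 20 and 24.

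The procedure sections say when the scores are taken. Section 5.6.10.1 names week 4: "Subjects will complete the Dermatology Life Quality Index (DLQI) at weeks 0, 4, 8, 12, 16, 20 and 24". Sections 5.6.6 and 5.6.8 are general: "IGA will be determined for all subjects throughout the study" and "BSA will be determined for all subjects throughout the study".

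The Schedule of Assessments marks IGA, BSA and DLQI at baseline and at weeks 8, 12, 16, 20 and 24, and leaves week 4 blank. Week 4 is marked for concomitant medications, adverse events, IP dispensing and accountability, and itch. The itch row reads "Itch NRS X X X X X X X", its seven marks running from baseline to week 24.

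**The concern.** Two inconsistencies sit together.

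First, the plan promises week-4 results that its own visit table does not collect. Site staff usually work from the table. If they do so here, there will be no week-4 IGA, BSA or DLQI, and a score not taken at the visit cannot be recovered. If they follow the text, nothing is lost. The documents do not say which takes precedence, so practice could also vary from subject to subject.

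Second, with two different secondary lists, either could later be presented as the prespecified one. The study is open-label, the investigator performs the analysis (Section 8.2) and self-monitors the records (Section 8.1), and a separate statistical plan is optional (Section 8.2.1). No later document is therefore certain to settle the matter.

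**Working it through.** The plan gives no figure to reproduce on this point, so the check is a count. Each secondary efficacy endpoint at each post-baseline week is one cell. Week 0 is left out because it is the baseline visit, where change is zero by definition.

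**Step 1. Count the cells in each list.**

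| Endpoint | Synopsis weeks | Cells | Section 8.2 weeks | Cells |
|---|---|---|---|---|
| IGA 0/1 | 20, 24 | 2 | 4, 8, 12, 20, 24 | 5 |
| 50% BSA reduction | 12, 16, 20, 24 | 4 | 12, 16, 20, 24 | 4 |
| Improvement in IGA, BSA, NRS, DLQI | 4, 8, 12, 16, 20, 24 | 4 × 6 = 24 | 4, 8, 12, 16, 20 | 4 × 5 = 20 |
| Total | | 30 | | 29 |

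**Step 2. Check each cell against the Schedule of Assessments.** The only cells without a scheduled assessment are at week 4.

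- Section 8.2: IGA 0/1 and improvement in IGA, BSA and DLQI, so 4/29 = 13.8%. The other 25 are scheduled.
- Synopsis: improvement in IGA, BSA and DLQI, so 3/30 = 10.0%. The other 27 are scheduled.

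These cells come from three assessments, since IGA 0/1 and IGA improvement use the same score. If the table is followed, 0 of about 20 subjects will have any of the three at week 4.

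**Step 3. Compare the two lists.**

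- Shared: 2 (IGA 0/1) + 4 (50% BSA) + 20 (improvement) = 26.
- Union: 30 + 29 − 26 = 33.
- Differing: 33 − 26 = 7, and 7/33 = 21.2%. Three are only in Section 8.2 (IGA 0/1 at weeks 4, 8 and 12). Four are only in the synopsis (week-24 improvement in the four measures).
- Of the 7, all but IGA 0/1 at week 4 have scheduled data.

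**Step 4. Is the blank a text-extraction fault?** Unlikely. Six rows share it (physical exam, BSA, IGA, DLQI, vital signs, photography), while four others are marked at week 4. Three of the six also conflict with the text outside the endpoints: Section 5.6.9 names week 4 for photography, and Section 5.6.5 asks for a physical examination with vital signs at every visit.

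**Step 5. Primary endpoint.** It is IGA 0/1 at week 16 in both the synopsis and Section 8.2, and IGA is marked at baseline and week 16.

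**The case against.** The case for treating this as minor has several parts.

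- **Only DLQI has week 4 named in the procedure text.** This is right. Scoring at screening, baseline and weeks 8 to 24 could pass for the general wording used for IGA and BSA. For those two, the explicit conflict is between the endpoint lists and the table, and it remains.
- **The blank may be a deliberately lighter visit.** Possibly. In that case both endpoint lists and Section 5.6.10.1 are wrong, and the conflict stays.
- **The count of 7 is inflated by one truncated line.** Section 8.2 runs from week 20 straight into adverse events, which is probably a drafting slip. With week 24 restored, the lists differ in 3/33 = 9.1% of cells, all for IGA 0/1. The percentages also depend on convention: counting the four week-0 entries in each list gives 4/33 = 12.1%, 3/34 = 8.8% and 7/37 = 18.9%. This is fair, but the unscheduled cells are the same under any convention.
- **The scope for selective reporting is small.** IGA improvement at weeks 4, 8 and 12 is in both lists, so those scores are already declared for analysis, and no formal test is specified. This limits the harm. It does not say whether the responder proportion at those weeks was prespecified.
- **Variation between subjects is conjecture in a single-center study.** Agreed: it is possible, but nothing in the documents shows it.
- **Improvement at week 0 is only wording.** Agreed. It biases nothing and needs only a tidy-up.

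**Conclusion.** The concern holds. The plan names secondary endpoints at week 4 that its schedule does not collect, and it gives two secondary lists that do not match. Three assessments at one visit are affected, feeding 4 of 29 cells in Section 8.2 and 3 of 30 in the synopsis. The loss is complete for those cells if the table is followed and nil if the text is followed; the documents do not settle which. The 7 differing cells are mainly a reporting matter, and 4 of them probably come from one slip.

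The counts take both lists as written, exclude week 0, and read the table's blank cells as intended. Neither the primary result nor the 50% BSA endpoint can change. This should be fixed because it is certain, cheap to repair and irreversible for week-4 data, but it does not threaten the study's main conclusion.

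**What to change.** Reconcile the synopsis endpoints, Sections 5.6.5 to 5.6.10.1, Section 8.2 and the Schedule of Assessments before week-4 visits and before analysis.

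1. **Week 4: choose one of two equally valid options.**
   - *Option A:* mark IGA, BSA, DLQI and photography at week 4 in the schedule.
   - *Option B:* if a lighter visit is intended, delete week 4 from IGA 0/1, from IGA, BSA and DLQI improvement, and from Sections 5.6.9 and 5.6.10.1. Replace the general timing in Sections 5.6.6 and 5.6.8 with the actual weeks. Keep week 4 for itch NRS.
2. **Under either option,** bring the physical exam and vital-signs rows into line with Section 5.6.5, and state whether table or text governs.
3. **Use one secondary list,** identical in the synopsis and Section 8.2. State the weeks for IGA 0/1 once, include week-24 change from baseline for all four measures, and drop week 0 as an improvement timepoint.
4. **If week-4 visits have already taken place without these scores,** report those cells as not collected.

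The cost is an edit to the table and wording. Option A slightly lengthens a visit that already takes place; the documents do not say by how much. Option B gives up the earliest response data on three measures.
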